This is consistent with the current gap in the literature with only a few studies investigating fall risk related to these types of drugs (15–17). Moreover, the group advocated for a higher research quality in primary studies due to issues with precise definitions of target medications and falls as well as lack of controlling for confounders (14,18). Therefore, to achieve a better understanding of these 17 medication classes as potential FRIDs, more studies taking these issues into account are warranted.

Primary objective:

To examine the association between use of the potential FRIDs and falls rate with a 1-year followup in a cohort of community-dwelling older adults, aged 75 years or more.

Study methods

Study design and sample size:

This prospective cohort study builds on previous data from the PREFALL study conducted in cooperation with Hjørring Municipality, Denmark (19). A pre-registered protocol on the PREFALL study was accepted at Clinicaltrials.gov (NCT03608709) on 01/08/2018 (20). The study recruited participants from 14/06/2018 to 18/07/2019 and had a 1-year follow-up period. The sample size was derived without a recommended power calculation; hence, the sample size builds on feasible recruitment within the 13 months inclusion period granted by the municipality due to economical and administrative reasons.

Timing of final analysis:

All study data were accessible from the PREFALL study before the completion of this protocol. Therefore, a detailed statistical analysis plan for this study was prepared before any outcome analysis was conducted to provide transparency on the intended and pre-planned analysis. This is prespecified later in the protocol.

Study population and setting

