The participants were community-dwelling aged 75 or more. Participants were excluded if they had 1) a dementia diagnosis; 2) acute illness defined by the presence of a participant-reported experience of illness within 7 days before inclusion affecting their ability to participate in social activities outside their homes; 3) inability to understand Danish; 4) Unable to stand unassisted for one minute. Support was defined by any assistive devices or help from another person. In Denmark, municipalities develop and initiate prophylactic and health-promoting initiatives for senior citizens (22). Thus, the participants were recruited through preventive home visits (PHV), senior activity centres (SAC), along with senior clubs and associations in Hjørring Municipality, Northern Jutland, Denmark. For PHVs, all the community-dwellers aged 75+ years who accepted the invitation to PHV were assessed for eligibility and included consecutively. For SACs, senior clubs, and senior associations, participants were conveniently recruited by oral study presentations since a

consecutive sampling method was not possible due to varying attendees each day. Lastly, recruitment videos were transmitted by the local televisions channel along with ads in newspapers and social media. For a more detailed description of the study setting and recruitment, the investigators refer to the PREFALL study (19).

Follow-up:

Follow-up time will be defined as the time from inclusion until death, withdrawal, or end of the study at the 18/07/2020. A summary of the participants' loss to follow-up will be presented with reasons and baseline characteristics to describe the adequacy of follow-up.

Baseline characteristics:

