Data collection was performed at baseline and based on a multifactorial falls risk test battery including various physical tests (static balance under dual-task conditions, grip- and lower limb strength, reaction time of lower limbs and gait speed); self-report questionnaire on sociodemographic characteristics, frailty, nutrition, disability, fear of falling, health-related quality of life, depressive symptoms, several physical symptoms, cognitive tests; and reporting of comorbidities (23). The participants' comorbidities were obtained from the participants' hospital records and the diagnoses were indexed according to the International Classification of Diseases 10th revision (ICD-10). For a more detailed description of physical test and self-report questionnaire and their rationale, the investigators refer to the PREFALL study (19).

Baseline medication:

To determine the participants' medications at inclusion, the investigators consulted the national Shared Medication Record (SMR). The SMR is a national registry of current medication use and pharmacy records of prescriptions to each citizen in Denmark. Any physician involved in the patients' clinical course has access to the SMR data and all details of each prescription and the date of the latest medication reconciliation are provided (24). For each participant all medication registered in SMR at baseline was documented and indexed according to the WHO-recommended anatomical therapeutic chemical (ATC) medication classification system. The potential FRIDs which will be investigated in this study are: Beta-blockers (C07A); angiotensin-converting enzyme (ACE) inhibitors (C09A); calcium channel blockers (C08); cardiac glycosides (C01A); antiarrhythmic drugs (C01B); laxatives (A06A); proton pump inhibitors (A02BC); antiparkinson drugs (N04); acetylcholinesterase inhibitors (N06DA); beta blocker eye drops (S01ED); corticosteroid (H02A); oral

hypoglycaemic drugs (A10B); vitamin D (A11CC05); nonsteroidal anti-inflammatory (NSAID) drugs (M01A); fluoroquinolones (J01MA); and antineoplastic agents (L01).

Confounding covariates:

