Many different risk factors and predictors for falls in older adults have been described previously and classified into different domains: sociodemographic, medical conditions, psychological, balance and mobility, and medication use (4,25,26). All these risk factors are possible confounders to the potential FRIDS; hence, the following a priori list specifies the confounding variables to be adjusted for in the multivariate regression model:

- Age (5,8).
- Sex (4).
- History of previous falls (19,27,28).
- The comorbidity related to the potential FRID to adjust for confounding by indication (18).
- Fear of falling using Short Falls Efficacy Scale-International 7-item (4,27–30).
- Gait speed measured with a 4-meter walk test (31–33).
- Cognitive impairment estimated by the Orientation-Memory-Concentration test performed over the telephone (4,27,33,34).
- Frailty using the Tilburg Frailty Indicator (35).
- Physical and instrumental disability in activities of daily living using the Vulnerable Elders Survey 13 (4,32,33,36).
- Depressive symptoms using Geriatric Depression Scale 4 item, a depression diagnosis or prescription of any antidepressants (4,16,27,28).
- Use of benzodiazepines, benzodiazepines derivatives or non-benzodiazepines (Z-drugs) (16,37).
- Use of opioids (15,38).

Statistical analysis

Outcome:

The primary outcome is fall rate per person-year. Fall rate will be calculated as the total number of falls divided by length of follow-up in years. A fall was defined as "an unexpected event in which the participants come to rest on the ground, floor, or lower lever" (39). Falls were recorded

prospectively with daily fall calendars with a monthly reporting and validated by a phone call if a fall was registered. If the calendar was not received within 14 days after deadline, the participant was contacted to retrieve the missing data.

Statistical methods:

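### Drug exposure is one baseline record applied to a year or more of falls, so the rate ratio for any class used in short courses is diluted, and no exposure window or sensitivity analysis is planned

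*Combined protocol and SAP*

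**What the plan says.** All references are to the combined protocol and SAP.

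- **Exposure** (Baseline medication). The purpose of the record check is stated as "To determine the participants' medications at inclusion". "For each participant all medication registered in SMR at baseline was documented and indexed" by ATC code. The source is described thus: "The SMR is a national registry of current medication use and pharmacy records of prescriptions to each citizen in Denmark". The section gives no look-back period, prescription duration or rule for calling a prescription active. Sixteen classes are listed, among them corticosteroids and "nonsteroidal anti-inflammatory (NSAID) drugs (M01A); fluoroquinolones (J01MA").
- **Follow-up.** Study design and sample size says: "The study recruited participants from 14/06/2018 to 18/07/2019 and had a 1-year follow-up period". The Follow-up section says: "Follow-up time will be defined as the time from inclusion until death, withdrawal, or end of the study at the 18/07/2020".
- **Outcome.** "Fall rate will be calculated as the total number of falls divided by length of follow-up in years". Falls were recorded "prospectively with daily fall calendars with a monthly reporting".
- **Model** (Statistical methods). One adjusted Poisson model per class gives an IRR, provided that more than 5 participants have a baseline prescription. The significance threshold is 0.05. Time-updated exposure, a risk window and a shortened follow-up are not mentioned.

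**The concern.** A baseline flag is a reasonable proxy for exposure when a drug is taken continuously. When it is taken for days or weeks, most of the person-time credited to users is off drug. The user group's fall rate then averages a short on-drug period with a long off-drug one, and the IRR moves towards 1 even if the drug raises fall risk while it is taken.

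The study exists to clarify whether unresolved classes increase fall risk, and the introduction criticises earlier work for imprecise definitions of the target medications. Applying one undefined baseline flag to both long-term and short-course drugs leaves that weakness in place for the second group. An IRR near 1 would be hard to interpret, because the plan has nothing to separate no effect from an effect diluted by time off drug.

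**Working it through.** The plan states no sample size, power or effect size, so there is no figure to reproduce.

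**Step 1: length of follow-up, from the plan's dates.**
- Last recruit: 18/07/2019 to 18/07/2020 = 366 days.
- First recruit: 14/06/2018 to 18/07/2020 = 765 days.

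The upper figure holds only if the common end date governs. If every participant is instead followed for one year, the 365-day column below applies.

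**Step 2: dilution.** Let the fall rate be constant off drug and multiplied by R on drug. With d exposed days in a window of W days and unexposed comparators:

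observed IRR = 1 + (d / W) × (R − 1)

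R and d are assumptions. For R = 2.0:

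| Exposed days after inclusion | W = 30 | W = 90 | W = 365 | W = 765 |
|---|---|---|---|---|
| 7 | 1.23 | 1.08 | 1.02 | 1.01 |
| 14 | 1.47 | 1.16 | 1.04 | 1.02 |
| 30 | 2.00 | 1.33 | 1.08 | 1.04 |
| 90 | 2.00 | 2.00 | 1.25 | 1.12 |
| 180 | 2.00 | 2.00 | 1.49 | 1.24 |
| Continuous | 2.00 | 2.00 | 2.00 | 2.00 |

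Example: 1 + (14 / 365) × 1 = 1.038. Varying R with 14 exposed days over 365: R = 1.5 gives 1.019 and R = 3.0 gives 1.077.

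The 7-day row matters because someone found mid-course at inclusion has, on average, about half the course left. A 14-day course then contributes about 7 days.

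**Step 3: what dilution does to power.** Assume 500 participants, 1 fall per person-year, no overdispersion, a two-sided 5% test and 365 days of follow-up. SE of log IRR = √(1/E1 + 1/E0), where E1 and E0 are expected falls in users and non-users.
- 20 users, undiluted IRR 2.0: E1 = 40, E0 = 480, SE = 0.165, power about 99%.
- 20 users, diluted IRR 1.04: E1 = 20.8, E0 = 480, SE = 0.224, power about 5%, which is the false-positive rate.
- 6 users, the fewest for which a model is fitted: about 66% undiluted and 5% diluted.

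**Step 4: what a short window can deliver, on the same assumptions.** Expected falls among 20 users with no drug effect:
- 30 days: 20 × 30/365 = 1.6. Power is about 9% for an IRR of 1.47 and 23% for 2.0.
- 90 days: 20 × 90/365 = 4.9, against 480 × 90/365 = 118.4 in non-users. SE = √(1/4.93 + 1/118.4) = 0.46, so the 95% interval spans the estimate divided and multiplied by exp(1.96 × 0.46), about 2.5.

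With 6 users, the expected falls are 0.5 at 30 days and 1.5 at 90 days. Short windows reduce dilution but lose much of the precision.

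**The case against.** The strongest reply is that the premise lies outside the documents. No section calls any class short-course or gives a duration, and the result turns on that. With 90 days of use or more, a true IRR of 2.0 still shows as 1.25 to 2.0 over a year. Sampling at one date also over-represents long-term users among those on drug that day. This stands, and it is why the point is conditional for NSAIDs and corticosteroids.

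Fluoroquinolones, the clearest case, may never be modelled. They need more than 5 baseline users, and the exclusion for illness in the preceding 7 days may remove some. This also stands.

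A short window is a weak remedy. A 30-day estimate could rest on one or two falls while the plan adjusts for a list of 12 covariates. At 90 days, a 14-day course is still diluted to between 1.08 and 1.16. If the record includes lapsed prescriptions, defining active use comes first. This stands too and limits the fix to one sensitivity analysis plus a descriptive estimate.

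Two stronger readings are tempting, and the documents support neither. A reader might infer that the planned IRR will be near 1 for these classes whatever the truth. Besides its dependence on duration, residual confounding by indication or repeat courses could move it away from 1. A reader might also infer that the authors will report a null as absence of risk. The plan does not say so: it declares a one-year association as its objective and gives only a p-value threshold.

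**Conclusion.** The concern holds in conditional form. It is certain from the text that exposure is read once, that falls are counted over all follow-up, and that no window, active-use rule or sensitivity analysis is planned. The size depends on assumed days of use: with R = 2.0 over 365 days, dilution is nearly complete at two weeks or less, large at 30 days, partial at 90 days and absent with continuous use. The calculation assumes a constant background rate, no carry-over effect and no later courses in either group.

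The 765-day figure worsens dilution but is not needed for the conclusion, and the one-year and common-end-date statements should be reconciled in any case. The 1-year IRR is a valid description of the association with holding a baseline prescription. For a class used briefly, it says little about risk during treatment.

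**What to change.** Keep the 1-year model as primary and add the following before any outcome analysis. The Timing of final analysis section says that the data were already accessible, so a window chosen after seeing results would carry little weight.

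1. Define exposure as a prescription active at inclusion, where the recorded prescription details allow, and say how other entries are handled.
2. Pre-specify one sensitivity analysis for all modelled classes, counting falls and person-time only in the first 90 days after inclusion.
3. For fluoroquinolones, NSAIDs and corticosteroids, report a 30-day estimate descriptively, and only where it can be estimated.
4. Report items 2 and 3 as estimates with confidence intervals, without significance claims. They add up to 16 + 3 = 19 estimates to a plan with an unadjusted 0.05 threshold.
5. State that the 1-year IRR refers to having a baseline prescription, so a value near 1 for a short-course class does not exclude risk during treatment.

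The cost is some re-coding of exposure and extra model runs. The daily calendars should already hold the fall dates, although the plan does not say whether these were entered in the analysis data. The main downside is few falls in the short windows: intervals will be wide, some classes may not be estimable, and even the 90-day estimate stays diluted for courses of about two weeks.

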Falls in community-dwelling older adults are a major public health issue with an annual incidence of approximately 30% among adults aged \geq 65 years increasing to 32-42% among those aged \geq 75 years (1). In addition, the number of fallers is expected to increase in the future since the proportion of older people over 60 years is increasing worldwide (2). In Europe, the most frequent reason for older adults to contact an emergency department is due to falls - accounting for 50% of the total contacts (3). Even though most of the falls result in minor injuries, an increasing proportion leads to fractures or hospitalization. Furthermore, consequences of falls include increased morbidity and mortality along with loss of independence, which may lead to early institutionalization (1,4,5). Finally, the increasing number of fallers also leads to increased financial burden on the health care system (6).

Although some falls have a single obvious reason, most falls have a multifactorial aetiology such as previous falls, advanced age, cognitive impairment, environmental risks, hazardous activities, along with presence of chronic disease, muscle weakness, gait and balance disorders, and medication use (1,4,7–13). Recently, The European Geriatric Medicine Society (EuGMS) Task and Finish Group published a consensus paper classifying 14 medication classes as fall-risk-increasing drug (FRID) (14). Most of them were psychotropics, but several new possible FRIDs were identified. However, the group did not reach consensus on 17 medication classes as potential FRIDs (antihypertensives, cardiac glycosides, antiarrhythmics, gastrointestinal agents, central nervous system agents, chemotherapeutics, hypoglycaemics, fluoroquinolones, corticosteroids, and nonsteroidal anti-inflammatory drugs). This was substantiated by the studies presented for the panellists being heterogenous due to various settings, different cohorts of older adults as well as unclear descriptions of the medication and falls ascertainment methods. Hence, the evidence was insufficient to attain consensus.

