A flowchart will be given to illustrate the flow of participants through the study including number of participants with and without falls. The participants' baseline characteristics and follow-up time will be summarised using descriptive statistics. Continuous variables will be summarized using medians with interquartile range, and categorical variables will be presented using counts and percentage proportions. Furthermore, the number of participants with missing data for the outcome, baseline characteristics, and confounding covariates will be presented. Then, missing data will be handled with multiple imputation methods. Finally, a univariate and multivariate Poisson regression model will be used to specify the association (expressed as incidence rate ratio, IRR) between the potential FRID and the rate of falls. For each potential FRID, a multivariate Poisson regression model will be performed adjusting for the medical indication of each drug and all other confounders from the a priori list. However, the Poisson regression model will only be performed for the potential FRID if more than 5 participants have a prescription registered at baseline. P-values lower than 0.05 will be considered as statistically significant. All statistical analyses will be carried out using R, version 4.0.2, (R Foundation).

Dissemination and reporting

The investigators want to publish the study in peer-reviewed journals in English. The reporting of the study will follow the Strengthening the Reporting of Observational studies in Epidemiology (STROBE) statement.

References:

- 2. Organization WH. WHO Global report on Falls Prevention in Older Age. Community Health. 2007.
- 3. EuroSafe. Injuries in the European Union, Summary on Injury Statistics 2012-2014. Amsterdam; 2016.
- 5. Rubenstein LZ. Falls in older people: Epidemiology, risk factors and strategies for prevention. Age Ageing. 2006;35(SUPPL.2):37–41.

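### Apart from depression and a cognitive test score, no disease other than the drug's own related comorbidity enters any model directly, so confounding by other fall-related illness is controlled only through proxies

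*Combined protocol and SAP*

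**What the plan says.** The opening background attributes most falls to several causes at once, among them "presence of chronic disease, muscle weakness, gait and balance disorders, and medication use". The section on confounding covariates then describes known risk factors as "classified into different domains: sociodemographic, medical conditions, psychological, balance and mobility, and medication use", and states: "All these risk factors are possible confounders to the potential FRIDS". From this it derives a fixed list of 12 items.

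Two of the 12 name disease. One is "The comorbidity related to the potential FRID to adjust for confounding by indication". The other is "Depressive symptoms using Geriatric Depression Scale 4 item, a depression diagnosis or prescription of any antidepressants". Cognition enters as a telephone test score. The remaining nine are age, sex, previous falls, fear of falling, gait speed, frailty, disability, benzodiazepines or Z-drugs, and opioids.

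The section on statistical methods confirms how the list is used. For each class, "a multivariate Poisson regression model will be performed adjusting for the medical indication of each drug and all other confounders from the a priori list". A class is modelled if it has more than 5 users at baseline.

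Under baseline characteristics, comorbidities are said to come from hospital records and to be coded in ICD-10. The plan does not use them for a comorbidity count, an index or a fixed set of fall-related diagnoses.

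**The concern.** Adjusting for a drug's indication deals with one route of confounding: people take the drug because of a disease that itself causes falls. It does not deal with a second route, in which users of the drug also carry more of other diseases that cause falls. Several of the listed classes, such as laxatives, proton pump inhibitors, vitamin D and corticosteroids, are used across many illnesses, so a single related comorbidity plausibly describes little of how their users differ from non-users. Co-medication does not fill the gap, since the only drugs adjusted for throughout are benzodiazepines, Z-drugs, opioids and, within the depression item, antidepressants.

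At stake is the adjusted IRR for each class. If users are sicker in ways that neither the indication nor the functional measures pick up, a class with no effect on falls will tend to show an IRR above 1. The study justifies itself partly by poor confounder control in earlier work, so leaving a named domain only indirectly covered is a weakness it can reduce with data in hand.

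**Working it through.** **Step 1: the domains against the list.**

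| Domain named in the plan | Items in every model |
|---|---|
| Sociodemographic | age, sex |
| Medical conditions | the drug's related comorbidity; depression diagnosis (within the depression item) |
| Psychological | fear of falling, depressive symptoms, cognitive test score |
| Balance and mobility | gait speed |
| Medication use | benzodiazepines or Z-drugs, opioids, antidepressants (within the depression item) |
| Across domains | previous falls, frailty, disability |

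The allocation to rows is mine; the plan does not assign items to domains. The medical conditions row has no term for general disease burden. Other disease is represented only by measures that disease may affect.

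**Step 2: how large the residual bias could be.** The plan states no sample size, prevalence or effect size, so there is no planned figure to reproduce, and every input below is an assumption. Take one omitted binary condition, another fall-related disease, with prevalence p1 in users and p0 in non-users, and with fall rate ratio RR. For a drug with no effect, the IRR shown is

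(1 + p1 × (RR − 1)) / (1 + p0 × (RR − 1)).

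The correct inputs are conditional ones: the prevalence gap and the RR that remain after frailty, disability, gait speed, cognition, previous falls and the other items are in the model. A low RR stands for proxies that absorb most of the disease effect, a high RR for proxies that absorb little.

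| Assumed p1 v p0 | RR 1.2 | RR 1.5 | RR 2.0 |
|---|---|---|---|
| 25% v 15% | 1.05/1.03 = 1.019 | 1.125/1.075 = 1.047 | 1.25/1.15 = 1.087 |
| 30% v 15% | 1.06/1.03 = 1.029 | 1.15/1.075 = 1.070 | 1.30/1.15 = 1.130 |
| 40% v 20% | 1.08/1.04 = 1.038 | 1.20/1.10 = 1.091 | 1.40/1.20 = 1.167 |

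The range is about 1.02 to 1.17. It is not a bound. A wider assumed gap of 50% v 20% with RR 2.0 gives 1.50/1.20 = 1.25, while 15% v 10% with RR 1.2 gives 1.03/1.02 = 1.01.

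**Step 3: what decides where in the range the truth lies.** It depends on how much of the disease effect the functional and frailty measures already carry. The documents give no information on this, and no planned analysis would reveal it.

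**The case against.** The strongest reply is that the adjustment set is already rich. Conditions such as Parkinson's disease or stroke plausibly raise the fall rate largely through gait, disability, cognition and a history of falls, all of which are in every model. People with a dementia diagnosis and those unable to stand unassisted for one minute were excluded, which removes part of the severe end. Each listed item has a supporting citation, and preferring a disease count over functional measures is partly a modelling choice. A count also gives every disease group equal weight, so it controls imperfectly for any one of them.

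Much of this stands. A reader might infer that other diseases go uncontrolled; they do not, and the problem is residual confounding. A reader might infer that every diagnosis is already coded; the text supports only diagnoses found in hospital records. It is also tempting to say which diseases a given drug's model omits, but the plan does not list which diagnoses count as related to which class, so such statements are inference. Nor does the plan contain a rule for labelling a class as fall-risk-increasing; its stated aim is to examine an association.

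What does not stand is that the proxies make a disease term unnecessary. They measure function, and a disease can raise fall risk by routes that a 4-metre walk or a frailty score need not register. The plan enters the indication, a depression diagnosis and cognition alongside frailty and disability, so it does not itself treat those scores as sufficient.

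**Conclusion.** The point holds as a gap in direct control. The plan treats medical conditions as possible confounders, holds coded comorbidities, and enters none of them beyond the drug's related comorbidity and depression. The resulting bias could be negligible (an IRR of about 1.02 for a null drug) or moderate (about 1.17). Those figures rest on the assumed prevalences and residual rate ratios above, and the documents neither size the bias nor show it to be material. This is an inexpensive improvement worth making, and the omission does not invalidate the planned models.

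**What to change.** Add one item to the a priori list, used in every drug's model: a count of ICD-10 chronic disease groups, or a standard weighted index, built from the hospital-record comorbidities already coded and excluding the indication of the drug under study. Choose between count and index in advance, name the disease groups, and say whether depression, which has its own item, is counted. Because the indication has to be excluded, the SAP must also fix which ICD-10 codes form the related comorbidity for each class. Report each IRR with and without the new term, so that readers can see whether any class's result depends on it.

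One summary term is preferable to separate indicators for individual diseases. A model may run with as few as 6 users and already carries 12 covariate items, and indicators entered only where user numbers seem to permit would bring a data-dependent choice into a prespecified list.

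The cost is SAP wording and about one degree of freedom per model, with no new data. Intervals will be slightly wider for classes with few users, and control stays partial because hospital records may miss conditions managed elsewhere. The plan says it was prepared before any outcome analysis. If that analysis has since begun, the added term should be reported as a sensitivity analysis and labelled as added later.

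### Recurrent falls are to be analysed by Poisson regression with no allowance for overdispersion, so with default standard errors the p-values will be too small in the univariate models and probably in the adjusted ones

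*Combined protocol and SAP*

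**What the plan says.** - **Outcome.** The Outcome section states: "Fall rate will be calculated as the total number of falls divided by length of follow-up in years". A person who falls four times contributes four events.
- **Model.** Under Statistical methods, "a univariate and multivariate Poisson regression model will be used to specify the association (expressed as incidence rate ratio, IRR" for each of the 16 listed drug classes. The adjusted model contains the drug's indication and the rest of a 12-item confounder list.
- **Decision rule.** "P-values lower than 0.05 will be considered as statistically significant".
- **Entry rule.** A class is modelled "if more than 5 participants have a prescription registered at baseline", so six users are enough.
- **Heterogeneity.** The Confounding covariates section opens with "Many different risk factors and predictors for falls in older adults have been described previously". The introduction also names, among the causes of falls, "environmental risks, hazardous activities, along with presence of chronic disease, muscle weakness, gait and balance disorders".

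Nowhere does the plan mention overdispersion, a dispersion check, a negative binomial or quasi-Poisson model, robust standard errors or a fallback model. It names R as the software but not the type of standard error.

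**The concern.** Poisson standard errors assume that, given the terms in the model, the variance of the count equals its mean. If people differ in their underlying fall rate for reasons outside the model, the variance is larger, the standard errors are too small and p-values are too low. Drug classes unrelated to falls would then be declared significant more than 5% of the time.

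This is the only inferential model for the primary objective, and it is applied to up to 16 classes. The Timing of final analysis section says that all data were already accessible when the plan was written. A variance estimator left open could therefore be chosen after results are seen.

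**Working it through.** **Inputs.** The documents give no sample size, mean fall rate, variance or power, so there is no figure of the plan's to reproduce. They do give the share of fallers ("increasing to 32-42% among those aged" 75 or more, read here as at least one fall in a year), the 5% level (taken as two-sided), 12 adjustment factors, 16 classes and the six-user minimum. Everything else below is assumed, including that the default Poisson variance is used.

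**Step 1: direction.** If person *i* has rate λᵢ, with mean μ and variance σ² across people, the count over one year has mean μ and variance μ + σ².
- *Univariate models:* if the 12 listed factors predict falls, as the plan says, leaving them out makes σ² > 0.
- *Adjusted models:* σ² = 0 only if the list explains all variation between people. The causes in the introduction's list that concern surroundings, risky activities, muscle weakness and balance are not on the confounder list as such. Yet the Baseline characteristics section says that "static balance under dual-task conditions, grip- and lower limb strength" were measured.

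**Step 2: large-sample size, unadjusted.** For a negative binomial count with dispersion *a*, variance/mean is φ = 1 + aμ. The share with no fall is (1 + aμ)^(−1/a) = 1 − p. The true size of the nominal 5% test is 2·[1 − Φ(1.96/√φ)]. With p = 0.37:

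| Assumed mean μ | a | φ | True size |
|---|---|---|---|
| 0.5 | 0.34 | 1.17 | 0.070 |
| 0.7 | 1.69 | 2.18 | 0.185 |
| 0.8 | 2.19 | 2.75 | 0.238 |
| 1.0 | 3.00 | 4.00 | 0.327 |

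The range starts at 5%. A pure Poisson with mean −ln(1 − p), that is 0.386, 0.462 or 0.545 for p = 0.32, 0.37 or 0.42, gives the same share of fallers with no overdispersion.

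**Step 3: univariate simulation.** The 12 covariates were the only source of heterogeneity, there was no drug effect and 20-60 people were users. Type I error was 0.067-0.073, 0.090-0.096 and 0.161-0.193 for an assumed log-rate SD of 0.5, 0.7 and 1.0.

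**Step 4: adjusted simulation.** Assumptions: 300 people, mean 0.8 falls per year, 12 normal covariates with log-rate SD 0.7, 7% with shorter follow-up, log follow-up offset, gamma residual dispersion, no drug effect and 2,000 replicates per cell. Replicates with no falls among users were excluded (at most 180 of 2,000). Type I error of the default Poisson test:

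| Residual dispersion | 6 users | 10 | 20 | 60 |
|---|---|---|---|---|
| 0 | 0.036 | 0.042 | 0.046 | 0.053 |
| 0.5 | 0.077 | 0.100 | 0.110 | 0.127 |
| 1 | 0.091 | 0.137 | 0.159 | 0.172 |
| 2 | 0.152 | 0.190 | 0.234 | 0.286 |

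A second simulation used other assumed inputs: 200 or 400 people, mean 0.6 and one covariate with log-rate SD 0.6. With 60 of 200 or 120 of 400 exposed, adjusted size was 0.045-0.047 at residual dispersion 0 and 0.09-0.24 at 0.5 to 2.

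**Step 5: across classes.** If all 16 classes were tested and null, expected false positives are 16 × 0.05 = 0.8 at the nominal level. At residual dispersion 1 they are 16 × 0.091 = 1.5 to 16 × 0.172 = 2.8.

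**Step 6: remedies in the step 4 runs.**

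| Method | Type I error |
|---|---|
| Negative binomial | 0.020-0.072 |
| Quasi-Poisson (Pearson-scaled) | 0.037-0.093 |
| Poisson, HC3 sandwich | 0.031-0.060 |
| Poisson, uncorrected HC0 sandwich | 0.066-0.123 (0.100-0.123 with 6 users) |

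**Imputation.** The planned multiple imputation was not simulated. It does not cure the problem: Rubin's rules add between-imputation variance, but the within-imputation part is still the Poisson one.

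**The case against.** **Sparse classes.** The inflation is not universal. With 6 to 10 users, mild heterogeneity and few falls, univariate size stays close to nominal: at log-rate SD 0.5 it was 0.046 with 6 users and mean 0.8, and 0.050 and 0.044 with 6 and 10 users and mean 0.5. This stands as a limit on size. It is a small-count effect, because the adjusted test with 6 users ran at only 0.036 when there was no overdispersion. Sparseness masks the error in those classes and does not remove it.

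**Adjusted models matter more.** Unadjusted IRRs are confounded by the plan's own account, so the firmer half of the argument concerns the less important analysis. The adjusted model includes previous falls, which directly mark a person's tendency to fall, as well as gait speed, frailty, disability and fear of falling. These may stand in for balance and strength. All this is fair, and it is why the adjusted claim is only that inflation is probable. Nothing on the list measures surroundings or risky activities, however, and the default standard error is right only if nothing at all is left over.

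**Undocumented dispersion.** Residual dispersions of 0.5 to 2 are assumptions, and the 32-42% figure alone fits no overdispersion. The count of 1.5-2.8 false positives needs all 16 classes to be tested and null. Both points stand and limit what can be said about size.

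**Choice of remedy.** HC3 errors held the level best in the simulation and keep the planned Poisson model. That is correct, and they are a sound alternative.

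**Conclusion.** The concern holds. As written, the plan's only inferential model for the primary objective understates uncertainty whenever fall rates vary beyond the model terms. For the univariate models this follows from the plan's own premise; for the adjusted models it is probable. The conclusion assumes default Poisson standard errors, since no other estimator is named.

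The direction is secure, but the size is not fixed by the documents. Under the step 4 assumptions, adjusted type I error runs from about 4-5% with no residual dispersion to 15-29% at dispersion 2, with less inflation in classes near six users. IRR point estimates remain consistent if the mean model is right; p-values and any intervals do not have their stated properties. Because this affects the primary inference and is cheap to correct, it should be changed before the analysis is run.

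**What to change.** In the Statistical methods section, replace Poisson regression by negative binomial regression with log follow-up time as offset, in both the univariate and multivariate models, keeping the IRR as effect measure. Name quasi-Poisson with Pearson-scaled standard errors as the fallback, for example if the negative binomial model does not converge.

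If Poisson with sandwich errors is preferred, specify a small-sample correction of HC3 type. Six users suffice for a model, and in the simulation uncorrected sandwich errors rejected 10-12% of the time there. In either case, state the variance estimator and report the estimated dispersion for each model.

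The cost is one or two sentences and a different R function, with no new data. Intervals will be wider and fewer classes will reach p<0.05. The negative binomial test is somewhat conservative in the smallest classes (0.020-0.036 with six users in the simulation).
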